## **3.11 Safety Analyses**

Safety summaries will be conducted on the Safety Population.

The following sections detail the summaries performed on the safety data. Additional data handling rules including those for imputation of partially missing dates are provided in a separate SAP document pertaining to data handling and programming specifications.

The baseline scores for laboratory assessments and local skin reactions will be the last non-missing value collected before first application of A-101 45% in this study. For most subjects, Visit 1 laboratory measurements in this study are done on Visit 13 of parent double-blind study (A-101-WART-301 or A-101-WART-302).

### **3.11.1 Extent of Exposure**

The duration of treatment, the number of application days (i.e. the actual count of days where an application occurred), the mean applications per wart (for each subject the sum of all applications across all treated warts and all application days divided by the total number of treatments for all treated warts), and the total applications will be summarized using descriptive statistics (n, mean, SD, median, minimum and maximum). The percentage of total wart treatments that were performed in 1, 2 or 3 applications is also provided.

Overall compliance is calculated as the total number of wart treatments performed during the treatment period (through date of last application to any wart) divided by the total number of wart treatments expected to be performed. The total number of warts treated is the sum of the retreatment and home application diary records completed times the number of warts assessed at baseline minus the number of warts scored as PWA=0 or having an LSR grade 3 at the most recent assessment (<= the date of the application).

### **3.11.2 Adverse Events**

Adverse events are coded using the MedDRA (Version 22) and are categorized by system organ class (SOC) and preferred term (PT). Only treatment emergent adverse events are included in summary tabulations (i.e. adverse events occurring within 30 days of each application of study medication). All adverse events are included in the data listings including those that are not considered treatment emergent.

To allow differentiation as to which study period an Adverse Event occurred, three categories are defined based upon onset date. Adverse Events that had onset dates prior to the first application of study medication are considered "prior". Adverse events with onset dates on or within 30 days of an application of study medication are considered "treatment emergent". Events with onset dates more than 30 days after the most recent application of study medication are considered as "post-therapy." In this study, subjects can possibly receive medication up to three cycles and multiple doses of medication within a treatment cycle. The above rule will be applied to all known doses of medication while determining study period.

Frequency tabulations are presented by MedDRA SOC and preferred term, for all adverse events; study treatment-related adverse events, adverse events resulting in discontinuation of study treatment, serious adverse events and adverse events by maximum severity. Adverse events resulting in discontinuation are those with 'action taken' recorded as 'drug withdrawn'.

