13.1.3. Adverse Event Reporting Period

The investigator must start reporting non-serious AEs starting with the subject’s first study medication treatment continuing until the subject’s last study visit. Non-serious adverse events that occur between the time the subject was consented and the first application of study medication will be reported as medical history.

Reporting for SAEs begins after the subject signs the informed consent and continues until the subject’s last study visit (regardless of relationship to study medication). If a subject experiences a SAE after the subject’s last study visit, that is deemed by the investigator to be related to study medication, the investigator must report this to the Sponsor using the study specific SAE report form.

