14.4. Statistical Analysis of Safety Data

Unless otherwise stated, all safety summaries will be conducted using the ITT population. All safety summaries will be produced for the following groups:

- Subjects treated in the study that were randomized to active treatment during the previous A101-WART 301/302 study.
- Subjects treated in the study that were randomized to vehicle during the previous A101-WART 301/302 study.
- Subjects treated in the study overall.
- Subjects not requiring treatment during the study that were randomized to active treatment during the previous A101-WART 301/302 study.
- Subjects not requiring treatment during the study that were randomized to vehicle during the previous A101-WART 301/302 study.
- Subjects receiving active treatment during the study or the previous A101-WART 301/302 study.

The proportion of subjects with treatment emergent adverse events will be tabulated and presented by System Organ Class and Preferred Term from the Medical Dictionary for Regulatory Activities (MedDRA). Likewise, the proportion of subjects with serious AEs will be summarized. Adverse event summaries will be presented showing the proportion of subjects experiencing adverse events, both overall and by MedDRA System Organ Class. The version of MedDRA to be used for the analysis of this study will be specified in the SAP.

Aclaris Therapeutics, Inc.

Protocol Number: A-101-WART-303

Protocol Version 3: 14 February 2019

Local skin reaction (LSR) scores and clinically relevant abnormal laboratory results will be tabulated and presented at the subject level. For each LSR sign and at each in-house visit, the proportion of subjects who had at least one treated wart with LSR severity ≥ 1 will be summarized.

Safety summaries will be supported by listings of all adverse events, laboratory results, and LSR data.

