### **3.11.3 Local Skin Reactions**

The number of subjects with local skin reaction signs or symptoms that worsened by at least 1 grade from baseline any time after the first application of study medication will be tabulated by treatment group for each LSR as well any LSR. A separate summary limited to LSRs that worsen and which occur within 30 days of the last application of study medication will be provided. Additionally, to assess effect of number of cycles of applications of study medication on LSR, this summary will be presented by treatment cycle also.

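### SAP 3.11.2 counts AEs and SAEs in tables only up to 30 days after an application, so later onsets in treated subjects of this long-term safety study are only listed; adding all-onset tables is a cheap improvement

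*SAP*

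**What the plan says.** SAP 3.11.2 sets the rule for AE tables: "Only treatment emergent adverse events are included in summary tabulations (i.e. adverse events occurring within 30 days of each application" of study medication). The planned frequency tables cover all AEs, related AEs, AEs leading to discontinuation, "serious adverse events and adverse events by maximum severity". None is exempted. On the remaining time after treatment the section says: "Events with onset dates more than 30 days after the most recent application of study medication are considered as" post-therapy. No table is assigned to that category; such events are in the listings.

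Collection runs longer. Protocol 13.1.3 has non-serious AEs reported from the "first study medication treatment continuing until the" last study visit. For serious events: "Reporting for SAEs begins after the subject signs the informed consent and continues until the" last study visit.

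Protocol 14.4 plans tables of treatment-emergent AEs without defining a window. It then says: "Likewise, the proportion of subjects with serious AEs will be summarized". A further sentence reads: "Adverse event summaries will be presented showing the proportion of subjects experiencing adverse events, both overall and by MedDRA System Organ Class". Neither gives an onset limit.

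For local skin reactions, SAP 3.11.3 tabulates signs or symptoms that "worsened by at least 1 grade from baseline any time after the first application of study medication", and adds a separate summary limited to 30 days from the last application.

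**The concern.** The primary objective is long-term safety and subjects stay for 6 months. Under SAP 3.11.2 a treated subject's AE or SAE that starts more than 30 days after the most recent application enters no incidence table, whatever its seriousness or judged relationship. Listings keep the event but give no proportion and no subject-time, so a 6-month AE or SAE proportion cannot be read from the tables.

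Two features of the protocol make late onsets relevant. Section 13.1.3 asks for SAEs judged related to be reported even after the last visit, so delayed drug-related events are not ruled out. And after Visit 1 the only scheduled blood draw is on Day 182; section 12.2 makes a clinically significant out-of-range result found after treatment begins an AE. If such an AE is dated at the draw, it is post-therapy for a subject with one course from Day 1, or with courses from Days 1 and 60. The shift tables would show the laboratory value, but no AE table would show the event.

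The label also covers time between courses: a subject about to be treated again can have an event flagged post-therapy.

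**Working it through.** The plan gives no figure for the period that the tables cover, so there is none to reproduce. The check is a count of days.

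**Inputs**
- Application days within a course: 1, 4, 8, 11, 15, 18, 22, 25, 29, 32, 36, 39, 43, 46, 50, 53 (protocol 10.5). The last falls 52 days after the course starts.
- Window: the application day and the next 30 days (SAP 3.11.2), applied to all known doses.
- Courses: up to three, started by Day 122 (SAP 3.3). End of study: Day 182.
- The start days below are assumed examples within these limits. Day 60 is the office visit at which a further course can be dispensed.
- Applications stop for warts that have cleared (protocol 9.2), so a last application before Day 53 is possible. Day 29 is used because the wart assessment follows that day's in-office application.

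**Formula.** For a course started on day s and completed, the last application is on day s + 52 and the window ends on day s + 82. Applications within a course are at most 4 days apart, so no gap opens inside one. The uncovered days are those from first application to Day 182 that lie in no window.

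| Pattern | Last application | Window ends | Uncovered days | Share |
|---|---|---|---|---|
| One course from Day 1 | 53 | 83 | 84–182: 182 − 83 = 99 | 99/182 = 54.4% |
| Day 1, last application Day 29 | 29 | 59 | 60–182: 182 − 59 = 123 | 123/182 = 67.6% |
| Courses from Days 1 and 60 | 112 | 142 | 143–182: 182 − 142 = 40 | 40/182 = 22.0% |
| Courses from Days 1 and 122 | 53, then 174 | 83, then 204 | 84–121: 121 − 83 = 38, all between courses | 38/182 = 20.9% |
| Courses from Days 1, 60 and 119 | 171 | 201 | none | 0 |
| One course from Day 42 | 94 | 124 | 125–182: 58 | 58/141 = 41.1% |
| One course from Day 84 | 136 | 166 | 167–182: 16 | 16/99 = 16.2% |

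In the last two rows the denominator runs from first application: 182 − 42 + 1 = 141 and 182 − 84 + 1 = 99.

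**Sensitivity.** If every application slips by the permitted day, the first row becomes 98/181 = 54.1%. With end of study on Day 184 (the maximum stay) it is 101/184 = 54.9%. A completed last course leaves no uncovered tail to Day 182 if s + 82 ≥ 182, that is, if it starts on Day 100 or later.

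**The case against.** **Nothing is hidden.** SAP 3.11.2 defines the window openly, flags every event and lists all of them. A 30-day treatment-emergent table is legitimate. Discontinuation for an adverse event is also tabulated as a disposition reason with no onset limit (SAP 3.5), and the AE-discontinuation table requires that drug was withdrawn, so few late events could enter it anyway. This stands: the point concerns counting, not loss of data.

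**The protocol is not contradicted.** A reader might infer that limiting the SAE table departs from protocol 14.4. The documents do not support that. The SAE sentence follows the treatment-emergent one and opens with the word 'likewise', which can carry the restriction over. Silence in the next sentence is not a contrary rule, and section 14 leaves details of all summaries to the SAP. What remains is that the protocol states no 30-day figure.

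**The gap is smallest with repeated courses.** The study rationale is repeated treatment (protocol 4.2), and in the examples two or three completed courses leave 0 to 22% uncovered. The parent studies also follow subjects for 12 weeks after their 8 weeks of treatment. This narrows the point but does not remove it: the sample-size argument counts a subject with prior active treatment and a single WART-303 course as repeatedly treated, and such a subject starting on Day 1 has at least 54% uncovered.

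**The table list mentions all adverse events.** It could be read as unrestricted, but the earlier sentence says that only treatment-emergent events are tabulated.

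**The skin-reaction contrast is imperfect**, since those are graded at visits and not by onset date. It shows only that the SAP uses the two-table layout elsewhere. The uncut laboratory shift tables are a weaker comparison still: with one scheduled draw on Day 182, a 30-day limit would empty them for most single-course subjects.

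**Conclusion.** The point holds as a cheap improvement to the outputs for the primary objective, not as an error or a breach of the protocol. For treated subjects, AE and SAE incidence is tabulated only up to 30 days after an application. The uncovered time to Day 182 ranges from 0 (three consecutive courses) to 54% (one full course from Day 1), and to 68% if applications end on Day 29. These figures assume the scheduled application days and the example start days.

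They measure time at risk. The documents give no AE rates, so they do not show how many events would be missed. A reader might also infer a study-wide total by applying the shares to the 148 subjects in the sample-size section. That cannot be supported: no mix of courses is given, the 26% behind the 148 refers to warts in the parent studies and not to subjects per course, and the 148 (200 × 0.74) is a minimum from the prior-active arm only.

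Nor is the labelling of events between courses undefined: SAP 3.11.2 applies its rule to all known doses, so they are post-therapy. The tabulation of subjects never treated in WART-303 is a separate population question and is not part of this point.

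**What to change.** Keep the 30-day treatment-emergent tables as planned. In SAP 3.11.2 add, for treated subjects, AE and SAE frequency tables for all onsets from the first WART-303 application to end of study. Split them by the existing treatment-emergent and post-therapy flags, show gaps between courses separately from follow-up after the last course, and give subject-time for each period so that the columns can be compared.

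The cost is SAP wording and a few tables. For treated subjects the events are already collected to the last visit and the flags are already defined, so no new data are needed. The downside is longer output and somewhat higher stated AE proportions in the all-onset tables; the retained 30-day tables keep the narrower figure available.

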4.2. Study Rationale

The rationale for the dose selection and treatment design of A-101-WART 301 and A-101-WART-302 and this open label, long term safety study is based on data collected from three completed (3) Phase 2 studies which assessed dose response and dose frequency of A-101 (H_2O_2) Topical Solution in patients with common warts. All three studies demonstrated good efficacy and safety of H_2O_2 45% for the treatment of common warts.

The three studies conducted are identified below and they represent data collected from 406 subjects.

- **Study A-101-WART-201:** A Randomized, Double-Blind, Vehicle-Controlled, Parallel- Group, Study of A-101 Solution in Subjects with Common Warts (n=90).
- **Study A-101-WART-202:** A Randomized, Double-Blind, Vehicle-Controlled, Parallel Group Study of A-101 Topical Solution Applied Once a Week in Subjects with Common Warts (n=157).
- **Study A-101-WART-203:** A Randomized, Double-Blind, Vehicle-Controlled, Parallel Group Study of A-101 Topical Solution Applied Twice a Week in Subjects with Common Warts (n=159)

Aclaris Therapeutics, Inc.

Protocol Number: A-101-WART-303

Protocol: Version 3: 14 February 2019

On the basis of these successful Phase II studies, Aclaris has progressed to phase III with studies A-101-WART 301 and A-101-WART-302. These studies will assess efficacy and safety of 8 weeks of treatment and 12 weeks of post treatment follow up. Aclaris recognizes that many patients may require multiple treatment courses and there is therefore a need to assess the long-term safety of topical H₂O₂ 45%. A-101-WART-303 is therefore designed to assess the long-term safety of patients who were initially treated in studies A-101-WART-301 and A-101-WART-302.

Aclaris Therapeutics, Inc.

Protocol Number: A-101-WART-303

Protocol: Version 3: 14 February 2019

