### 1. STUDY OBJECTIVES

#### 1.1 Primary Objective

The primary objective of this study is to evaluate the long-term safety of A-101 45% when applied twice weekly to common warts.

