### **3.13 Sample Size**

The sample size is based on an estimate of how many subjects will be required to provide at least 100 subjects requiring repeated treatment for a wart over the course of the study.

- By recruiting 400 subjects, we estimate 200 subjects will have received active treatment in the A101-WART 301/302 studies.
- We expected approximately 26% of warts treated in A-101-WART-301/302 studies to be clear at the end of the A-101-WART-301/302 studies.
- Based on the assumption that 26% of warts will be clear, at least 148 subjects will require exposure to active treatment.
- We anticipate that some subjects originally randomized to vehicle (in double-blind studies) will be exposed to active treatment.

As a result, the study should exceed the target of exposing more than 100 subjects to repeated treatments over the course of the study.

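### The planned adverse event tables do not show incidence by treatment cycle, although the study's rationale is safety under repeated courses

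*SAP*

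**What the plan says.** The objective in SAP 1.1 is general: "The primary objective of this study is to evaluate the long-term safety of A-101 45% when applied twice weekly to common warts". Protocol 4.2 gives the reason for the study: "many patients may require multiple treatment courses and there is therefore a need to assess the long-term safety". SAP 3.13 sizes it on a count of subjects, "required to provide at least 100 subjects requiring repeated treatment for a wart over the course of the study".

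SAP 3.3 allows up to three treatment cycles, the last starting no later than Day 122. It defines a period study day so that data can be referred to each cycle.

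For adverse events, SAP 3.11.2 states: "Frequency tabulations are presented by MedDRA SOC and preferred term, for all adverse events", and then for related, treatment-ending and serious events and by maximum severity. One 30-day treatment-emergent rule runs over all doses in all cycles. Protocol 14.4 also tabulates by System Organ Class and Preferred Term within parent-study groups, and names no cycle factor. Under SAP 3.2, Safety Population summaries have two columns: open-label A-101 after double-blind A-101, and open-label A-101 after double-blind vehicle.

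For local skin reactions, SAP 3.11.3 takes the other course: "to assess effect of number of cycles of applications of study medication on LSR, this summary will be presented by treatment cycle also". SAP 3.10 gives the primary and all four secondary efficacy endpoints by cycle.

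**The concern.** The study exists because patients may need several courses. The natural safety question is whether a second or third course carries more risk than the first. The SAP asks this of local skin reactions and not of adverse events.

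The by-cycle skin reaction table does not fill the gap. Protocol 12.1 has skin reactions scored before application at treatment visits, and has any reaction in the 20 minutes after an in-office application recorded as an adverse event. Acute post-dose reactions therefore fall in the tables that have no cycle view. So do systemic events.

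With one pooled proportion per column, a rise in risk with repeat courses looks the same as a flat risk observed for longer. Subjects scheduled for at most 16, 32 or 48 applications (one, two or three cycles of 16) share one denominator.

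**Working it through.** **1. The plan's own figure.** Inputs from SAP 3.13: "By recruiting 400 subjects, we estimate 200 subjects will have received active treatment in the A101-WART 301/302 studies" and "We expected approximately 26% of warts treated in A-101-WART-301/302 studies to be clear". 200 × (1 − 0.26) = 148, which matches the stated figure and exceeds 100. This counts A-101 in the parent study followed by A-101 in this study. Second and third cycles within this study are not counted.

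**2. What pooling hides.** Take subjects who have all three cycles, with assumed per-cycle risks that are independent across cycles. Pooled incidence = 1 − Π(1 − p).
- Rising 10%, 15%, 20%: 1 − 0.90 × 0.85 × 0.80 = 38.8%
- Falling 20%, 15%, 10%: 1 − 0.80 × 0.85 × 0.90 = 38.8%
- Constant: 1 − 0.612^(1/3) = 15.1% per cycle, again 38.8%

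One pooled number fits all three patterns. The same happens with a mix of one and two cycles. Assume 148 treated, of whom 110 start cycle 2.
- Constant 10%: (38 × 0.10 + 110 × 0.19)/148 = 16.7%
- 10% then 20%: (38 × 0.10 + 110 × 0.28)/148 = 23.4%
- Constant 14.3%: (38 × 0.143 + 110 × (1 − 0.857²))/148 = 23.4%

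The last two cannot be told apart.

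**3. Time at risk by cycle.** Inputs: applications on Days 1 to 53 of a cycle, the 30-day rule, Visit 5 at Day 60 with dispensing for a new cycle, and the final visit at Day 182. Assume back-to-back cycles started at Visit 5.

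| Cycle | Start | Last application | 30-day window ends |
|---|---|---|---|
| 1 | Day 1 | Day 53 | Day 83 |
| 2 | Day 60 | Day 112 | Day 142 |
| 3 | Day 119 | Day 171 | Day 201 |

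The cycle 1 window overlaps cycle 2, and the cycle 3 window passes Day 182. If events go to the cycle of the most recent application, a subject who restarts on Day 60 gives cycle 1 59 days (Days 1 to 59). A subject who stops after cycle 1 gives 83 days. Cycle 3 gives at most 64 days (Days 119 to 182). With a constant daily hazard that yields 10% over 83 days (assumed), 59 days yields 1 − 0.9^(59/83) = 7.2% and 64 days yields 1 − 0.9^(64/83) = 7.8%. Unadjusted by-cycle proportions can therefore differ with no change in hazard.

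**4. Selection into cycle 2.** Protocol 7.3 and 13.2.3 allow withdrawal for an adverse event. Assume a constant 10% risk, a share s of cycle 1 cases who do not continue, and all non-cases continuing. Cycle 1 risk among continuers = 0.10(1 − s)/[0.10(1 − s) + 0.90].
- s = 10%: 0.09/0.99 = 9.1%
- s = 50%: 0.05/0.95 = 5.3%

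Against 10% in cycle 2, this looks like a rise where there is none.

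**5. Precision of a by-cycle row.** At an assumed 10% risk, the approximate 95% half-width, 1.96 × √(0.09/n), is ±4.8 points for n = 148, ±5.9 for 100, ±6.8 for 74 and ±9.7 for 37. On the schedule in step 3 a third cycle starts at Day 119, three days before the Day 122 limit, so few subjects are likely to reach it.

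**The case against.** The strongest reply is that the planned tables do address repeat exposure as the study defines it. The sizing counts A-101 in the parent study followed by A-101 here, and the Safety Population columns split on that axis. If 100 to 200 prior-vehicle subjects are treated (assumed), a two-sided 5% comparison with 148 prior-active subjects would have about 56% to 74% power for 20% against 10%, although no test is planned. The objective is long-term safety and does not name a cycle-response comparison. The protocol lists adverse events, skin reactions and laboratory tests without ranking them. Skin reactions are given by cycle, exposure is summarised, and all adverse events are listed, so a by-cycle table could be derived later.

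Much of this stands. A reader might infer that a study sized for repeat exposure cannot show anything about adverse events under it. The documents do not support that, because the column split gives a descriptive contrast on the exposure that was counted.

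The contrast is only a partial substitute. Each column mixes one, two and three cycles. Prior-active subjects who need treatment are largely those whose warts did not clear on active drug, so the columns differ by selection. Neither column compares a second course with a first within this study. A table derived from listings after the fact is also weaker than a prespecified one.

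**Conclusion.** The point holds as a gap in reporting. SAP 3.11.2 and Protocol 14.4 give no adverse event incidence by cycle, while the SAP gives skin reactions and efficacy that way and the rationale is multiple courses. The planned tables remain valid, and sample size is unaffected. This is a change worth making, not a flaw that defeats the study.

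The size cannot be fixed from the documents, which give no adverse event rate and no expected number of subjects per cycle. The 38.8% example shows the ambiguity and predicts nothing. A reader might take 16.7% against 23.4% as an expected effect. It is not one. The 110 reuses the 26% wart-level clearance at the end of the parent studies as if it were the share of subjects stopping after cycle 1 here. The 148 covers only the prior-active group, and the plan expects some prior-vehicle subjects to be treated too.

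A reader might also infer that comparing cycles within subjects who had at least two would remove selection. Step 4 shows that it would not.

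**What to change.** In SAP 3.11.2, add summaries of treatment-emergent, related, severe and serious adverse events by cycle of onset, within treatment group.

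- **Attribution:** assign each event to the cycle of the most recent application, and state how an event on the first day of a new cycle is handled.
- **Denominator:** subjects starting that cycle.
- **Exposure adjustment:** report rates per subject-time beside the proportions. Time at risk runs from the first application of the cycle to the earliest of the next cycle's first application, 30 days after the last application, or the last visit.
- **Cycle 1 shown twice:** for all treated subjects and for those who went on to cycle 2. A footnote should say that the second set leaves out subjects who stopped after a cycle 1 event and so can itself suggest a rise.

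Keep the existing pooled tables. No new data are needed, because application and onset dates already drive the treatment-emergent rule and period study day is already defined. The cost is a few extra tables and their programming. Cycle 3 rows will be small and should be read as descriptive only.
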